12.3.2 Exploratory endpoints

1. In this exploratory aim, all inflammatory markers and cytokine levels will be summarized using descriptive statistics at baseline and 15 weeks. The changes in inflammatory biomarkers will be assessed using one sample t-test of the difference (or sign test). Linear models will examine the association between the 8 and 15-week worst pain score (controlling for baseline worst pain score and change in pain worst pain) and baseline and 8 and 15-week inflammatory markers and cytokines. Normalizing transformations will be used if required.^{58, 59} We are limited in the number of covariates in each model based on sample size, so we will be careful of overfitting recognizing that patient and disease characteristics may be confounders in analysis. No correction for multiple comparisons will be applied based on the hypothesis generating nature of the aim.

2. In this exploratory aim, all questionnaire scores will be summarized using descriptive statistics at baseline and 15 weeks. The changes in survey responses will be assessed using one sample t-test of the difference (or sign test). We will use a linear model to examine the association between the 15-week worst pain severity (as measured by the BPI) and the baseline worst pain severity, and baseline and 15-week FM score. Similarly, separate models of the 15-week worst pain score will control for baseline worst pain severity and assess associations with baseline and 15-week PANAS scores and catastrophizing scores. We are limited in the number of covariates in each model based on sample size, so we will be careful of overfitting recognizing that patient and disease characteristics may be confounders in analysis. No correction for multiple comparisons will be applied based on the hypothesis generating nature of the aim.

3. We will report the proportion of individuals with undetectable levels of estrone and estrone sulfate at baseline and 15 weeks with corresponding exact binomial 95% confidence intervals. The exact levels of estrone and estrone sulfate at baseline and 15 weeks will be summarized using descriptive statistics.

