1.3 Exploratory Objectives

- 1. To examine the impact of 15 weeks of CBD therapy on inflammatory biomarkers in patients with breast cancer taking aromatase inhibitor therapy
- 2. To examine demographic, clinical, psychosocial, and inflammatory predictors of response to CBD therapy

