12.3 Statistical Analyses

12.3.1 Primary endpoint

The primary endpoint is defined as the absolute change in BPI worst pain from baseline to 15 weeks. This change will be reported with the corresponding 95% confidence interval. Differences from baseline at each time point for worst pain will be summarized via mean and standard deviation. Patient reported outcomes will be analyzed using linear mixed effects models and include a subject-specific random effect to account for the natural heterogeneity across patients. Normalizing transformations will be used if necessary to ensure accurate model fit.

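### The exploratory marker–pain model adjusts for an undefined change in worst pain; with the absolute 15-week change, every marker coefficient in the week-15 pain model is zero by construction

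*Combined protocol and SAP*

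**What the plan says.** Section 12.3.2 (Exploratory endpoints), item 1, sets out the analysis as follows: "Linear models will examine the association between the 8 and 15-week worst pain score" and the inflammatory markers and cytokines at baseline, week 8 and week 15, "controlling for baseline worst pain score and change in pain worst pain". It does not say over which interval the change runs, or whether it is absolute or percent. It adds "Normalizing transformations will be used if required", without naming the variable to be transformed.

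Two sentences in Section 12.3.1 bear on what the change could be. One is "The primary endpoint is defined as the absolute change in BPI worst pain from baseline to 15 weeks". The other is "Differences from baseline at each time point for worst pain will be summarized via mean and standard deviation", so a baseline-to-week-8 difference will also exist.

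Item 2 of the same exploratory section uses a different form for questionnaires: "separate models of the 15-week worst pain score will control for baseline worst pain severity", with no change term.

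Item 1 serves the inflammatory part of the second exploratory objective in Section 1.3: "To examine demographic, clinical, psychosocial, and inflammatory predictors of response to CBD therapy".

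**The concern.** A follow-up score is the baseline score plus the change between the two. A model for the follow-up score that already contains both leaves nothing for any other predictor to explain. An analyst who resolves the undefined term from the plan itself would most naturally take the primary endpoint's change, and would then get a week-15 pain model that cannot show a marker association however strong it is.

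A false conclusion is unlikely, because an R-squared of 1 would be noticed at the first fit. The harm is what follows: the covariates would be chosen again with the data in hand, across several markers, in an analysis for which "No correction for multiple comparisons will be applied based on the hypothesis generating nature of the aim".

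**Working it through.** The plan gives no figure for this model, so there is none to reproduce. Write Y0, Y8 and Y15 for worst pain at baseline, week 8 and week 15, M for the marker or markers at any time point, D15 = Y15 − Y0 and D8 = Y8 − Y0.

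**1. The identity.** Y15 = 1·Y0 + 1·D15 for every patient. Least squares of Y15 on Y0, D15 and M therefore gives coefficients 1, 1 and 0 with no residual, provided the design has full rank. This needs no assumption about the data. It applies to baseline, week-8 and week-15 markers alike.

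**2. Six-patient example** (invented data, to show the algebra only):

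- Y0: 4, 5, 6, 7, 8, 9
- Y15: 2, 6, 3, 7, 4, 8
- D15: −2, 1, −3, 0, −4, −1
- M: −1.2, 0.8, −0.7, 1.1, −0.5, 0.9

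| Model | Marker coefficient | R-squared |
|---|---|---|
| Y15 on Y0 + M | 2.06 | 0.977 |
| Y15 on Y0 + D15 + M | 0 | 1 |
| D15 on Y0 + M | 2.06 | 0.963 |

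The third row shows that using change as the outcome, with baseline as covariate, keeps the marker coefficient. The 2.06 is not a magnitude for this trial: marker and week-15 pain correlate at 0.965 in these data.

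**3. The other interval.** Because D8 = Y8 − Y0, adjusting for Y0 and D8 is the same as adjusting for Y0 and Y8; likewise Y0 and D15 is the same as Y0 and Y15.

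| Change used | Week-15 pain model | Week-8 pain model |
|---|---|---|
| Baseline to week 15 | identity, marker 0 | estimable, but conditions on later pain |
| Baseline to week 8 | estimable, but adjusts for week-8 pain | identity, marker 0 |
| Each model's own interval | identity, marker 0 | identity, marker 0 |

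**4. Percent change or a transformed outcome.** These need assumed data. One set of simulations used 40 patients (the evaluable number in Section 12.2), baseline pain drawn with mean 6.5 (Section 12.2) and an assumed SD of 2, rounded and held to 4–10, and an assumed effect of the week-15 marker on week-15 pain of 0.8 points per unit. In one data set:

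- baseline and markers only: week-15 marker coefficient 1.39, R-squared 0.70;
- absolute 15-week change added: 0, R-squared 1;
- percent change to week 15 added: 0.10, R-squared 0.97, a fall of 1 − 0.10/1.39 = 93%;
- baseline-to-week-8 change added: 1.27, R-squared 0.78;
- log(pain + 1) as outcome with raw 15-week change: 0.002 on the log scale, R-squared 0.95.

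Over 2,000 simulated trials, power for the week-15 marker was 78% with no change term, 76% with the baseline-to-week-8 change and 14% with percent change. A separate check with 40 patients and other assumed correlations gave a median marker coefficient of 0.88 without the term and 0.07 with percent change, a fall of 1 − 0.07/0.88 = 92%.

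These sizes depend on the assumptions. In the six-patient data, for instance, adding percent change lowers the marker coefficient only from 2.06 to 1.53. If outcome, baseline and change are all put on one transformed scale, the exact identity of step 1 returns.

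**The case against.** The strongest reply is that the plan does not say which change is meant, so exact failure follows only when the primary endpoint's definition is carried into a garbled phrase. That stands. A reader might infer that the model must fail as written; the text does not support this, because percent change, a transformed outcome and a mismatched interval all give models that can be fitted. It does not rescue the phrase, since none of those readings gives the baseline-adjusted marker–pain association at both time points.

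The phrase may also be a slip, for change in the marker or for change in pain as an alternative outcome. Item 1 cites two references whose titles concern difference scores, so such scores were in the authors' minds. The references follow the transformation sentence and their content is not available here, so they settle nothing. The words still say pain and still need correcting.

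Two cautions on the simulations are fair. The floor of 4 is a screening criterion (Sections 5.1.4 and 10.1), and the study calendar repeats the BPI at a baseline visit up to 4 weeks later, so baseline pain may be lower. And a high whole-model R-squared does not show that the change term takes most of the variation, because baseline and marker contribute too. The loss is therefore judged above by the marker coefficient and its power.

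**Conclusion.** The point holds, and it is minor. Item 1 adjusts for a change in worst pain that it does not define. Under the most natural reading, the absolute baseline-to-week-15 change with untransformed scores, every marker coefficient in the week-15 pain model is 0 and R-squared is 1. That result is algebra and rests on no assumed data beyond a full-rank design. With percent change, or a transformed outcome and raw change, the coefficients are not exactly zero, but the marker association was largely removed in the 40-patient scenarios (92–93% lower coefficients with percent change); that size is illustrative.

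Two wider inferences are not supported. The inflammatory part of the objective is not wholly lost: item 1 also plans a week-8 pain model, which remains estimable under the 15-week change, although it then conditions on later pain. Nor are the trial's main results at risk: the primary, secondary and safety analyses, the tests of marker change and the item 2 models do not use this covariate.

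**What to change.** Remove change in worst pain from the covariates in item 1. Fit separate linear models for week-15 and for week-8 worst pain, each on baseline worst pain plus the marker, as item 2 does. Equivalently, take change in worst pain to that time point as the outcome with baseline worst pain as covariate; the marker coefficients are the same.

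If change in the marker was intended, say so and state its interval. Do not enter it together with both the baseline and the follow-up marker on the same scale: with an intercept those terms have rank 3 of 4. If adjustment for pain at another visit was intended, state that as a separate question.

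The cost is one phrase, with no effect on data collection, sample size or conduct. It should be settled before the marker data are analysed.

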13 REGISTRATION GUIDELINES

Study related screening procedures can only begin once the patient has signed a consent form.

Patients must meet all of the eligibility requirements listed in Section 5 prior to registration. All eligibility will be reviewed and confirmed by PI or co-I prior to enrollment.

Patients must be registered before receiving any study treatment and must begin study treatment within 4 weeks of registration. See study calendar (section 9) for details.

14 DATA SUBMISSION SCHEDULE

The Case Report Forms (CRFs) are a set of (electronic or paper) forms for each patient that provides a record of the data generated according to the protocol. These forms will be completed on an on-going basis during the study. The medical records will be source of verification of the data. The CRFs will be completed by the Investigator or a member of the study team as listed on the Delegation of Duties Log.

15 SPECIAL INSTRUCTIONS

15.1 Patient-reported questionnaires

Prior to the first time the patient completes the questionnaires: Patients should be directed to report all symptoms and limitations whether or not they are related to the cancer or its treatment. They should also be told that their treating provider will not be told about symptoms that they report on the questionnaires, and they should mention them during their visit.

When patients are completing them at the time of the clinic visit, it is permissible to assist patients with completing the questionnaires being careful not to influence the patient's response. Discourage family members from influencing patient responses to the questions.

The study coordinator will review the questionnaires after completion on paper to ensure that no questions were accidentally skipped or that more than one answer was provided. Whenever possible, questionnaires will be completed online, although if a patient states that she is unable or unwilling to complete the questionnaire online then a paper form will be provided.

If a patient is unwilling to complete the questionnaires at the time of the study visits (baseline, week 8, and week 15) and has not yet done so within 2 working days following the visit, the study coordinator will follow-up with the patient by phone to remind her to complete the questionnaires. The questionnaires should be completed electronically, or the study coordinator can have the patient answer the questions by phone. They should be completed within 2 days after the baseline visit and within 7 days after week 8 and 15 visits.

For the assessment times that are not linked with a study visit, patients will be sent an email link via REDCap to questionnaires 2 days before each assessment time weeks 1-6 and 12. If they have not completed the questionnaire by the scheduled assessment time (based on date of CBD initiation) they will be sent a reminder by email and/or phone. If they do not answer the questions by 2 days after the assessment they will be contacted by the study coordinator to complete them by phone.

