e. Height and weight at screening visit. If these values have been documented in the medical record within 90 days they do not need to be repeated. f. Questionnaires will be completed electronically within 2 days before the scheduled visit, at the time of the visit, or within 2 days after the visit. It is preferable to have patients complete the questionnaires before or at each visit. Emailed reminders will be sent to patients from REDCap, and telephone reminders may also be used. If a scheduled visit is rescheduled after the questionnaires have been completed by the patient, they will not be considered out of window. If a patient declines to complete questionnaires electronically they may be completed on paper (baseline and week 8 and 15) or by phone (all timepoints).

g. It is preferred, but not required, that subjects fast for at least 8 hours prior to all blood collections (except for week 4). Time of blood draw and fasting status should be recorded. Details about research labs are in section 15.2.1.

h. Study medication should begin the first Wednesday morning after the baseline visit whenever possible. If the baseline visit is on a Wednesday, the participant can start the study medication the evening of the baseline visit. The medication should be taken with food twice a day approximately 12 hours apart.

i. At weeks 8 and 15 or off study, patient will meet with research study coordinator or otherwise return the medication log and/or remaining medication to the study team, depending on the timepoint. Patient does not need to be seen by physician or advanced practice provider. Patients will return medication log #1 at the 8 week study visit and return all remaining study drug and medication log #2 at the 15 week study visit, or at the off study visit if it occurs at a different time. If they forget to bring the medication and log to the visit, they should return the items at their next routine clinic visit.

j. For patients who wish to continue on therapy beyond the 15 week study visit, clinicians can provide a written prescription for off-label Epidiolex and/or provide recommendations for patients to go to local cannabis dispensaries in Michigan (since recreational cannabis is legal in this state), but drug will not be provided by the clinical trial following the week 15 study visit.

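### The week-15 BPI, which carries the primary endpoint, may be completed up to 7 days after the visit at which study drug is returned, so its 7-day recall can fall partly or wholly after dosing

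*Combined protocol and SAP*

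**What the plan says.** Section 10.2 bases the primary endpoint on BPI worst pain over the previous 7 days. Section 12.3.1 defines it as the absolute change from baseline to 15 weeks. Section 12.2 analyses by intention to treat and counts every patient who completes the 15-week BPI as evaluable.

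Two places set the time allowed for the week-15 form:

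- Section 9, footnote f, opens the window 2 days before the visit and closes it soon after: "at the time of the visit, or within 2 days after the visit". It adds a preference: "It is preferable to have patients complete the questionnaires before or at each visit".
- Section 15.1 deals with patients who do not answer at the baseline, week-8 or week-15 visit. The coordinator telephones a patient who "has not yet done so within 2 working days following the visit". The limit is then: "They should be completed within 2 days after the baseline visit and within 7 days after week 8 and 15 visits".

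On drug, footnote i tells patients to "return all remaining study drug and medication log #2 at the 15 week study visit", with a concession: "If they forget to bring the medication and log to the visit, they should return the items at their next routine clinic visit". Under footnote j the trial supplies nothing after that visit, and clinicians may prescribe the product off label or point patients to dispensaries. Section 7.3 sets treatment at 15 weeks, plus or minus 7 days, without reference to the BPI. The calendar column for week 15 runs from 2 days early to 7 days late.

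**The concern.** A late form does no such harm at week 8, because dosing continues. At week 15 the drug is due back at the visit, so each day of delay can replace a recall day on treatment with one off treatment. A patient seen on day 105 who hands back her drug and answers on day 112 complies with section 15.1 and is inside the calendar column, yet her whole recall period follows the end of dosing. Her form enters the primary analysis as the result of 15 weeks of CBD, and no analysis rule identifies it.

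If pain returns once dosing stops, such forms pull the mean change towards zero. If the patient has moved to a prescribed or dispensary product under footnote j, the form may reflect that product instead. The trial has a single arm, so no control group shares the error. The two windows also disagree, which leaves staff without one rule for the form that matters most.

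**Working it through.** **1. The plan's own power figure.** Inputs from section 12.2: n = 40, SD 3, two-sided 5%, effect 0.45 SD or 1.4 points, power 80%. A one-sample t-test on the change, using the noncentral t, gives 79.3% at 0.45 SD (1.35 points) and 82.1% at 1.4/3 = 0.467 SD. The stated 80% is reproduced to rounding.

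**2. Recall days off dosing.** Assume the last dose is at the visit. A form completed d days later has d of its 7 recall days off dosing: 2 of 7 at +2 and 7 of 7 at +7.

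**3. Plasma exposure over the recall.** Section 3.1.4 gives a half-life of 56 to 61 hours. With single-exponential decay, k = ln 2/(56/24) = 0.297 per day or ln 2/(61/24) = 0.273 per day. Mean exposure as a share of steady state = [(7 − d) + (1 − exp(−k·d))/k]/7.

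| BPI after last dose | Recall days on dosing | Mean exposure |
|---|---|---|
| at the visit | 7 of 7 | 100% |
| +2 days | 5 of 7 | 93% |
| +3 days | 4 of 7 | 86% |
| +5 days | 2 of 7 | 66-68% |
| +7 days | 0 of 7 | 42-45% |

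Carry-over is substantial, so the treatment effect is more likely diluted than lost.

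**4. When a late form would be taken.** If the section 15.1 call is made on the second working day after the visit, it falls at +2 to +4 days. If it is made on the working day after that, it falls at +3 to +5. Footnote h says "Study medication should begin the first Wednesday morning after the baseline visit whenever possible", so day 105 is usually a Wednesday and the call then falls at +2 or +5.

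**5. Illustrative effect on the primary result.** The documents give neither the share of late forms nor any relation between exposure and analgesia. Both are assumed here: a late form loses benefit in proportion to lost exposure (14% at +3, 33% at +5, 56% at +7), and the SD stays at 3. Mean change = 1.4 × (1 − share late × loss).

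| Share late | Timing | Mean change | Power |
|---|---|---|---|
| none | – | 1.40 | 82% |
| 10% | +3 days | 1.4 × (1 − 0.10 × 0.14) = 1.38 | 81% |
| 10% | +5 days | 1.4 × (1 − 0.10 × 0.33) = 1.35 | 79.5% |
| 5% | +7 days | 1.4 × (1 − 0.05 × 0.56) = 1.36 | 80% |
| 10% | +7 days | 1.4 × (1 − 0.10 × 0.56) = 1.32 | 77.5% |
| 20% | +7 days | 1.4 × (1 − 0.20 × 0.56) = 1.24 | 72% |

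With no analgesic loss, every row stays at 1.40 and 82%.

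**6. Could dosing simply continue until the form is done?** At full dose (section 7.1.2) weeks 1 to 3 use 3.5 + 7 + 10.5 = 21 mL, and later days use 2 mL each. Day 105 needs 21 + 2 × 84 = 189 mL; day 112 needs 21 + 2 × 91 = 203 mL. Two 100 mL bottles (section 7.1.1) run out at 21 + 179/2 = day 110.5. The supply does not reach day 112.

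**The case against.** The strongest reply is that the 7 days is a rescue limit. In section 15.1 it follows the provision for patients who do not answer at the visit, and the realistic alternative is a missing primary endpoint among 40 evaluable patients. That stands, and it is why the limit should be kept. It does not settle the conflict with footnote f, and even 2 days leaves 2 recall days off dosing.

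A second reply is that off-drug recall already belongs to an intention-to-treat analysis: footnote d has early stoppers continue questionnaires through week 15. This stands as a reason to keep every form in the primary analysis. It does not explain why a completer's form should slip off treatment for lack of a timing rule. Footnote d itself asks for the off-study questionnaires within 3 business days of stopping, which is tighter than the 7 days for completers.

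A reader might also infer that week 15 is chased later than other time points. For weeks 1-6 and 12 the text does say: "If they have not completed the questionnaire by the scheduled assessment time (based on date of CBD initiation) they will be sent a reminder". But the coordinator's completion call at those weeks also waits until 2 days after the assessment. Footnote f already provides emailed reminders, optional telephone reminders and a preference for completion before or at the visit. The chase rules are therefore nearly alike, and the comparison does not support a separate criticism.

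**Conclusion.** The gap is real. A compliant completer can give a week-15 BPI that describes only days after dosing, two sections disagree on how late it may be, and no rule links the last dose to the form. The expected consequence is modest dilution in an unknown, probably small, share of patients.

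A reader might infer that the trial loses ten points of power. The fall from 82% to 72% needs 20% of forms late, all at +7 days, with benefit lost in step with exposure. With 10% late and answered on a rescue call at +3 to +5 days, power is about 81% to 79.5%, close to the stated 80%. None of these shares is in the documents.

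The direction is not certain either. Footnote j permits other products, forgotten drug may be returned later, and mean plasma exposure is only a rough guide to a worst-pain item. No stated figure is wrong, and the evaluable set is unaffected. This is a cheap improvement of low to moderate priority.

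**What to change.** 1. In footnote i and section 15.1, require the week-15 BPI between 2 days before the visit and the visit itself, and before study drug is collected. If it has not been done, the coordinator takes it at the visit or by telephone the same day; footnotes f and k already allow telephone completion.
2. Make footnote f and section 15.1 agree: completion by the visit as the routine, with up to 7 days afterwards as a rescue limit only, so that no primary data are lost.
3. Keep every week-15 BPI in the primary analysis, including those from early stoppers. Add a sensitivity analysis that leaves out completers' forms given more than 2 days after the last dose, using the drug diary (section 7.1.3) and the BPI date.

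Do not extend dosing past the week-15 visit to wait for the form. Full-dose supply ends at day 110.5, and dosing would run beyond the last scheduled safety laboratory tests, although section 8.1.1 requires stopping for raised transaminases.

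The cost is a few lines of wording, slightly earlier reminders and one extra sensitivity analysis. Sample size, drug supply and the primary analysis do not change.
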